Severe Bleeding (EXCLUDED FROM THIS PROTOCOL): (arterial, venous, or mixed) that is rapidly flowing, pulsatile or spurting that in the surgeon's judgment requires rapid control to prevent hemodynamic consequences (e.g. hypovolemia, tachycardia, or hypotension) and could involve major volume loss which if not treated rapidly could be life threatening. EVARREST or SURGICEL should not be used in place of sutures or other forms of mechanical ligation for the treatment of major arterial bleeding.

PROCEDURE:

The TBS will be identified during the dissection related to the primary operative procedure. This will be the site assessed for haemostatic effectiveness.

Once the TBS is identified, the surgeon will immediately randomise the subject into the study. The randomly assigned treatment (EVARREST or SURGICEL) will be applied immediately at the actively bleeding TBS. The size of the treatment article applied should be sufficient for coverage of the entire TBS, and should overlap the bleeding source with a margin of 1-2 cm.

Randomised Subjects

After placement of the assigned study treatment (EVARREST or SURGICEL), firm manual continual manual compression will be applied over the entire bleeding area until 4 minutes from randomisation. The surgeon may use a surgical sponge (laparotomy pad or surgical gauze) to assist in providing adequate pressure over the entire surface area.

Haemostasis is defined as no detectable bleeding at the TBS. Absolute time to haemostasis, defined as the absolute time elapsed from randomisation to the last moment in time at which detectable bleeding at the TBS is observed, will be recorded.

Haemostasis will be assessed at 4 minutes from randomisation by carefully releasing manual compression and removing the surgical sponge (if used). Haemostasis will also be assessed at 10 minutes from randomisation and absolute time to haemostasis will be recorded.

For patients assigned to EVARREST, the EVARREST should not be removed once bleeding has been stopped.

For all subjects, if bleeding requiring treatment occurs after the 4 minute assessment the surgeon can revert to their standard of care for treatment.

Additional Treatment Impact on the Success/Failure of Endpoints

- Any additional treatment at the TBS after the 4 minute endpoint will be considered a failure for the 4 minute secondary endpoint.
- Any additional treatment after the 10 minute time point will be considered a failure for the 10 minutes secondary endpoint.

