2. STUDY OBJECTIVES

The objective of this study is to evaluate the safety and haemostatic effectiveness of the EVARREST versus control (SURGICEL ORC) as an adjunct to controlling mild to moderate soft hepatic parenchyma or soft tissue bleeding during open hepatic, abdominal, pelvic, retroperitoneal, and thoracic (non-cardiac) surgery in paediatric population.

The primary endpoint will be the absolute time to haemostasis, defined as the absolute time elapsed from randomisation to the last moment in time at which detectable bleeding at the TBS is observed.

The secondary endpoints of this study include:

- Proportion of subjects achieving haemostatic success at 4 minutes following randomisation and no bleeding requiring treatment at the TBS occurs any time prior to final fascial closure
- Proportion of subjects achieving haemostatic success at 10 minutes following randomisation and no bleeding requiring treatment at the TBS occurs any time prior to final fascial closure
- Portion of subjects with no re-bleeding at the TBS.
- Incidence of adverse events that are potentially related to bleeding at the TBS;
- Incidence of adverse events that are potentially related to thrombotic events;
- Incidence of re-treatment at the TBS;
- Incidence of adverse events
- Summarization of Haemoglobin, Haematocrit, Platelets laboratory results, estimated intraoperative blood loss and number of blood products transfusions

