HAEMOSTASIS ASSESSMENT (TIME TABLE):

T₀	Start time when randomisation envelope is opened
T_{APP}	Time when haemostatic product is initially applied with manual compression
T₄	TBS Bleeding assessment 4 minutes following randomisation. Note: Manual compression must be maintained from application until this initial assessment.
T₁₀	TBS Bleeding assessment 10 minutes following randomisation.
T_{ABS}	Absolute time to haemostasis; as defined as the absolute time elapsed from randomisation to the last moment in time at which there is detectable bleeding at the TBS

7.1.3.1 Adverse events from start of randomisation, including any complications potentially related to bleeding and/or thrombotic events.

7.1.3.2 Additional procedural and hospital stay information will also be recorded including surgery procedural times, blood product usage, blood transfusions, ICU time, estimated blood lost, cell saver use, surgical procedure/reason for surgery and alternative/additional methods used to achieve haemostasis (if applicable).

7.1.3.3 Additional surgical details will be captured for a liver only TBS, including estimated total transected plane area; estimated transected plane area treated (0-25%, 26-50%, 51-75%, 76-100%); reason for, type and location of liver resection; hepatic parenchymal classification/type; and surgeon description of bleeding site at the TBS (area, density, arterial/venous/mixed, and characterisation of intensity of flow).

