8.3.2 Methods of Analysis

Descriptive statistical analysis will be conducted overall, based on treatment and by paediatric groups (1 month (\geq 28 days from birth) to <1 year and $1\leq 18$ years). Primary endpoint data will also be summarized into Infants and toddlers (28 days to 23 months), Children (2 to 11 years) and Adolescent (12 to <18 years).

Two-sided 95% confidence intervals (CIs) for median absolute time to haemostasis will be reported separately for EVARREST and SURGICEL groups. In addition, for success/failure secondary endpoints (4 and 10 minutes haemostasis endpoints), two-sided 95% CI will be reported for P_F , P_C and for ratio P_F/P_C where P_F is the proportion of success in EVARREST subjects and P_C is the proportion of success in control subjects. The lower limits of these 95% CI will be utilized for statistical inferences.

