2. STUDY DESIGN

This is an open label, prospective, randomized, multicentre, controlled, clinical study comparing EVARREST to SURGICEL [oxidized regenerated cellulose (ORC)] (Control) as an adjunct to hemostasis when conventional methods of controlling mild or moderate bleeding are ineffective or impractical during surgery in pediatric patients.

At least 40 qualified pediatric subjects with an appropriate mild or moderate bleeding Target Bleeding Site (TBS) will be randomized in a 1:1 allocation ratio to either EVARREST or SURGICEL. Absolute time to hemostasis at the target bleeding site will be assessed as well as hemostasis at 4 and 10 minutes from randomization.

Enrollment will be staggered by age, as required by the European Medicines Agency (EMA) Paediatric Committee. The first 36 subjects enrolled will be aged ≥ 1 years to < 18 years of age. Enrollment of a subsequent group including 4 subjects from 1 month (≥ 28 days from birth) to < 1 year of age will follow. Ongoing safety assessment will ensure adequate safety monitoring occur during the staged enrollment.

The Target Bleeding Site (TBS) will be defined as the first accessible mild or moderate bleeding site identified in the hepatic parenchyma or soft tissue, where conventional methods of controlling bleeding are ineffective or impractical, and is amenable to manual compression. Once the TBS is identified, the surgeon will immediately randomize the subject into the study. The randomly assigned treatment (EVARREST or SURGICEL) will be applied immediately at the actively bleeding TBS.

EVARREST can only be used on a single TBS to be evaluated. If additional soft tissue or hepatic parenchymal bleeding sites are identified, the surgeon should treat according to their standard of care.

Randomization will be used to avoid bias in the assignment of treatment to each subject, to increase the likelihood that attributes of the subject are balanced across treatment groups, and to enhance the validity of statistical comparisons across treatment groups.

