8.2 Primary effectiveness analysis

The primary effectiveness endpoint is absolute time to hemostasis, defined as the absolute time elapsed from randomization to the last moment in time at which detectable bleeding at the TBS is observed.

The primary effectiveness endpoint will be summarized descriptively by treatment group. The primary endpoint will also be summarized descriptively by treatment group and pediatric group [1 month (≥ 28 days from birth) to <1 year and 1<18 years], as well as treatment group and age group [Infants and toddlers (28 days to 23 months), Children (2 to 11 years), and Adolescent (12 to <18 years)]. In addition, 95% distribution-free confidence intervals (CIs) for median absolute time to hemostasis will be reported separately for EVARREST and Control groups.

Absolute time to hemostasis will also be analyzed descriptively separately for subjects who achieved hemostasis with and without additional randomized treatments being required.

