8.2.1 Sample size justification

No formal sample size calculation has been performed for this study. The sample size required for the trial is at least 40 randomized paediatrics subjects recruited from sites within the European Union and Canada. This sample size is considered adequate to achieve the study objectives and provide sufficient information to evaluate data descriptively.

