8.3 Secondary effectiveness analysis

The following secondary effectiveness endpoints will be summarized descriptively by treatment group for the FAS:

- Proportion of subjects achieving hemostatic success at 4 minutes following randomization and no bleeding requiring treatment at the TBS occurs any time prior to final fascial closure;
- Proportion of subjects achieving hemostatic success at 10 minutes following randomization and no bleeding requiring treatment at the TBS occurs any time prior to final fascial closure;
- Proportion of subjects with no re-bleeding at the TBS.

Two-sided 95% CIs for the proportions of subjects with hemostasis at 4 minutes and 10 minutes will be constructed for each treatment group separately (P_E for EVARREST and P_C for Control), using the Clopper-Pearson method. In addition, for each time point, a two-sided 95% CI will be reported for the ratio proportion of successes (hemostasis achieved) in the EVARREST group/proportion of successes in Control group (P_E/P_C), using the Farrington-Manning score method.

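### The primary endpoint, absolute time to haemostasis, gets no EVARREST-versus-SURGICEL estimate, and its per-arm medians can depend on a recording convention that the documents do not show

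*SAP*

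**What the plan says.** - **Primary analysis.** SAP 8.2: "95% distribution-free confidence intervals (CIs) for median absolute time to hemostasis will be reported separately for EVARREST and Control groups". Protocol 8.3.2: "Two-sided 95% confidence intervals (CIs) for median absolute time to haemostasis will be reported separately for EVARREST and SURGICEL groups". The entry for Table 14.2.1 in SAP 10.2.2 repeats the per-arm intervals. None of these names a between-arm quantity.
- **Objective and design.** Protocol section 2 sets out to evaluate "haemostatic effectiveness of the EVARREST versus control". SAP section 2 describes a "controlled, clinical study comparing EVARREST to SURGICEL".
- **Secondary endpoints.** For haemostasis at 4 and at 10 minutes, SAP 8.3 adds to the per-arm intervals that "a two-sided 95% CI will be reported for the ratio proportion of successes (hemostasis achieved) in the EVARREST group/proportion of successes in Control group".
- **Sample size.** None was derived. SAP 8.2.1 calls 40 subjects "considered adequate to achieve the study objectives and provide sufficient information to evaluate data descriptively".
- **Measurement.** The endpoint runs from randomisation to the last moment at which bleeding at the target site is observed. The first scheduled look is at release of compression: "Haemostasis will be assessed at 4 minutes from randomisation by carefully releasing manual compression and removing the surgical sponge" (protocol synopsis). The time table in protocol 7.1.3 adds: "Manual compression must be maintained from application until this initial assessment". In both arms' instructions, protocol 7.1.3 also equates the endpoint with complete haemostasis.

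**The concern.** The trial randomises in order to compare two products, yet its primary endpoint ends in two intervals that the reader must compare by eye. Two secondary endpoints are better served. The stated objective therefore has no planned estimate on the endpoint chosen to address it.

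The by-eye comparison is also fragile. Under continuous compression, the moment when bleeding stopped is normally hidden for anyone dry at release. Read literally, the definition gives roughly the application time, since that is normally when bleeding was last seen. The gloss about complete haemostasis leaves 4:00 possible. For one subject the two readings differ by 240 s minus application time: 225 s if application is at 15 s, 120 s if at 120 s. The bleeding indicator listed in SAP section 7 starts only at 4 minutes, so it does not settle the matter.

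**Working it through.** The plan derives no figure for this endpoint, so there is none to reproduce. The checks below use these inputs.

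*From the documents:* at least 40 subjects, 1:1, so about 20 per arm. In the integrated earlier studies (protocol section 1), 89.9% of EVARREST and 49.4% of control subjects were dry at 3 or 4 minutes, and 97% and 78.3% by 10 minutes. These rates pool settings, severities and comparators, so they serve only as assumptions.

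*Assumed:* application time uniform over 20–60 s or 15–120 s, equal in the arms; stopping times uniform over 240–600 s for subjects dry between 4 and 10 minutes and over 600–1200 s for later ones. A typical value is the median over 20,000 simulated trials.

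**1. How far the EVARREST interval rests on the convention.** With n = 20, the distribution-free 95% CI for a median runs from the 6th to the 15th ordered time: coverage 1 − 2·P(Bin(20, 0.5) ≤ 5) = 0.959. If 89.9% are dry at the first look, P(at least 11 of 20 dry) > 0.9999 and P(at least 15 dry) = 0.988. So the EVARREST median almost surely, and its whole interval with probability 0.988, consist of values set by the convention. The typical EVARREST display is 240 s (240–240) under 4:00, 42 s (32–52) under application time at 20–60 s, and 73 s (48–99) at 15–120 s.

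**2. Gap between medians (SURGICEL minus EVARREST).** The control dry rate is varied, with the control 10-minute rate held at 78.3%.

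| Control dry at 4 min | 4:00 | Application, 20–60 s | Application, 15–120 s |
|---|---|---|---|
| 30% | 148 s | 347 s | 314 s |
| 49.4% | 22 s | about 135 s | about 135 s |
| 60% | 0 s | 11 s | 30 s |
| 70% | 0 s | 6 s | 17 s |

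The dependence is large at 30% and 49.4% and small at 70%.

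**3. A between-arm estimate that suits these data.** Let θ = P(E < C) + ½·P(E = C), the probability that an EVARREST subject has the shorter time. Split each arm into dry at first look, dry between then and 10 minutes, and later:

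- EVARREST: 0.899; 0.970 − 0.899 = 0.071; 0.030
- Control: 0.494; 0.783 − 0.494 = 0.289; 0.217

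Two subjects in the same class contribute ½, either as ties (4:00) or by symmetry (application time with equal handling). Then

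θ = 0.899(0.247 + 0.289 + 0.217) + 0.071(0.1445 + 0.217) + 0.030(0.1085) = 0.677 + 0.026 + 0.003 = 0.706.

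The value is the same under both conventions, but only because equal handling was assumed. The same sum gives 0.800 at a 30% control rate and 0.606 at 70%. Typical Brunner-Munzel 95% CIs at 49.4% are 0.57–0.84 (4:00), 0.53–0.89 (20–60 s) and 0.53–0.88 (15–120 s), with simulated coverage of 94.0–94.6%.

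**4. If handling speed differs by arm.** Under application time, an EVARREST difference of −20, −10, +10 or +20 s gives θ = 0.87, 0.80, 0.61 or 0.54 in the 20–60 s window, and 0.78, 0.75, 0.67 or 0.63 in the 15–120 s window. Coverage falls to 90.5% in the most extreme case (−20 s, 20–60 s). Under 4:00 there is no effect.

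**5. Alternatives.** A Hodges-Lehmann shift is exactly 0 s in about 56% of trials under 4:00 because of ties. Judging by whether two separate median intervals overlap is weak: with normal data and 20 per arm, non-overlap picks up a 1 SD shift in 34% of trials, against 85% for a rank-sum test.

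**The case against.** The plan is openly descriptive, protocol and SAP agree, and nothing is miscalculated. A reader might infer that the analysis is wrong, or that the trial cannot compare its arms. The documents support neither: the lack of a formal test is a declared choice, and the 4- and 10-minute ratios do compare the arms. But descriptive intent does not rule out a between-arm interval, as those ratios show.

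The new estimate may add little. Under 4:00 it correlates about 0.98 with the 4-minute risk difference. Under application time the correlation is about 0.77 and handling speed enters. This stands as a limit on interpretation. No document supports a handling difference: both products lie ready in the sterile field, and protocol 6.1.4 says EVARREST needs no preparation.

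A reader might also infer that the endpoint has no recording rule. That goes too far. The literal definition points away from 4:00, absolute time is listed separately from the 4-minute assessment, and protocol 7.1.3 contemplates breakthrough bleeding at any time after application. A rule may also sit in the CRF or the table templates, which are not shown. This is why the recording point is secondary.

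Finally, changing recorded primary values late in an open-label trial would invite suspicion, since the SAP's change log shows that deviations have already been assessed. That stands, and the fix leaves recorded values alone.

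**Conclusion.** The main point holds: the primary endpoint has no planned between-arm estimate, although the objective is comparative and two secondary endpoints have one. This is an omission worth correcting, not an error of calculation. It does not depend on the recording question or on any assumed rate.

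The secondary point holds conditionally. The medians can depend on the convention, but a reader who took the 49.4% row as the general size would overstate it. The effect ranges from a shift in the gap of roughly 170–200 s (148 to 314–347 s) at a 30% control rate to 6–17 s at 70%. These sizes rest on 20 per arm, the pooled earlier EVARREST rates and the assumed application windows. This trial admits only mild or moderate bleeding, so its control rate may differ from the pooled 49.4%.

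**What to change.** All changes are to the SAP, with no test and no change in sample size.

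1. In SAP 8.2 and Tables 14.2.1.1 and 14.2.1.2, add one prespecified descriptive estimate on the FAS, with the PP set supportive: the Mann-Whitney probability that an EVARREST subject has the shorter time, ties counted half, with a Brunner-Munzel 95% CI, using times as recorded.
2. Before database lock, state which convention the CRF instructions used for subjects dry at 4:00. Leave recorded values unchanged in the primary analysis. Repeat item 1 with those subjects set to the other convention. In-text table T3 (SAP 10.2.1) already mentions a sensitivity summary, and SAP 8.2 defines none beyond the supportive PP set.
3. Read the estimate beside the application times and 4-minute status by arm. Table 14.1.3.4 already plans both, so no new table is needed.

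The cost is a short clarification and one or two table rows from data already collected. The remaining price is interpretive: under 4:00 the estimate largely repeats the 4-minute comparison, and under application time it partly reflects handling speed.

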Any EVARREST re-treatment must be performed according to the Investigator's Brochure.

All subjects will have haemostasis assessed at 10 minutes after randomisation and have absolute time to haemostasis recorded regardless of any additional treatments.

EVARREST can only be used on a single TBS to be evaluated. If additional soft tissue or hepatic parenchymal bleeding sites are identified, the surgeon should treat according to their standard of care.

TEST PRODUCT: EVARREST Sealant Matrix/ EVARREST Fibrin Sealant Patch

STUDY

POPULATION:

Paediatric subjects, undergoing non-emergent abdominal, retroperitoneal, pelvic, hepatic or thoracic (non-cardiac) surgery procedures, wherein an appropriate TBS is identified. For this study paediatric subjects for this study are defined as; Infants and toddlers (28 days (1 month) from birth to 23 months), Children (2 to 11 years) and Adolescent (12 to less than 18 years).

New born infants (0-27 days from birth) are excluded from this study. Pre-term births are excluded from this protocol until the subject reaches 28 days from 37 weeks of pregnancy as determined by the investigator.

PRIMARY

ENDPOINT: Absolute time to haemostasis defined as the absolute time elapsed from randomisation to the last moment in time at which detectable bleeding at the TBS is observed.

SECONDARY

ENDPOINTS:

- Proportion of subjects achieving haemostatic success at 4 minutes following randomisation and no bleeding requiring treatment at the TBS occurs any time prior to final fascial closure
- Proportion of subjects achieving haemostatic success at 10 minutes following randomisation and no bleeding requiring treatment at the TBS occurs any time prior to final fascial closure
- Proportion of subjects with no re-bleeding at the TBS
- Incidence of adverse events that are potentially related to bleeding at the TBS;
- Incidence of adverse events that are potentially related to thrombotic events;
- Incidence of re-treatment at the TBS;
- Incidence of adverse events
- Summarization of Haemoglobin, Haematocrit, Platelets laboratory results, volume of blood loss, & volume of blood and blood products transfusions

SAFETY:

Adverse events will be collected from time of randomisation, throughout the follow-up period. Intra-operative bleeding at the TBS after 10 minutes will be an adverse event.

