1. INTRODUCTION

Bleeding during surgical procedures may manifest in many forms. It can be discrete or diffuse from a large surface area. It can be from large or small vessels; arterial (high pressure) or venous (low pressure) of high or low volume. It may be easily accessible or it may originate from difficult to access sites. The bleeding tissues may be firm or friable.

Conventional methods to achieve haemostasis include use of surgical techniques, sutures, ligatures or clips, and energy-based coagulation or cauterisation. When these conventional measures are ineffective or impractical, adjunctive haemostasis techniques and products are typically utilized, including topical absorbable haemostats such as oxidized regenerated cellulose, gelatin, or collagen and active haemostats such as topical thrombin or fibrin sealants.

Fibrin sealants are typically dual component systems consisting of virus-inactivated, human plasma-derived thrombin and fibrinogen. The two components are mixed during application to a target site and upon combination mimic the final step in the coagulation pathway to form a stable, physiological fibrin clot that assists in healingⁱ. The fibrinogen component may also contain anti-fibrinolytic agents. Fibrin sealants have proven to be valuable adjuncts for haemostasis in a variety of surgical and endoscopic procedures. They have been successfully used as biodegradable tissue adhesives for haemostasis, wound healing, or tissue sealing purposes in cardiovascular, thoracic, neurologic, gastrointestinal, urologic, gynaecologic, hepatic and plastic and reconstructive surgical procedures^{ii,iii,iv,v,vi}. They have also been evaluated in bleeding from soft tissue tumour beds following surgical resection^{vii}. Fibrin sealants have been shown to reduce post-operative complications, including blood loss and reduce the need for repeated procedures by promoting wound healing^{viii}.

The requisite preparation time for lyophilised products can be impractical and furthermore the use of fibrin sealants can complicate the application of pressure to the bleeding site, in that applied pressure can disrupt the sealant bond or cause the sealant to adhere to gloves or gauze. Application of fibrin sealants to actively bleeding sites can result in the sealant lifting or floating off the target site^{ix}, particularly in high volume or high pressure bleeding.

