6.4 Concomitant Medications

6.4.1 Topical Haemostats

The use of any other topical haemostats or fibrin sealant/fibrin sealant patch will be permitted and must be used according to the surgeon's usual practice. Details of all topical haemostats used for the subject throughout the procedure will be recorded on the Concomitant Medication CRF.

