8.3 Effectiveness

8.3.1 Effectiveness Variables

The following primary endpoint will be analysed using the FAS/ITT and Evaluable set:

- Absolute time to haemostasis defined as the absolute time elapsed from randomisation to the last moment in time at which detectable bleeding at the TBS is observed.

The following secondary endpoints will be analysed using the FAS/ITT set only:

- Proportion of subjects achieving haemostatic success at 4 minutes following randomisation and no bleeding requiring treatment at the TBS occurs any time prior to final fascial closure
- Proportion of subjects achieving haemostatic success at 10 minutes following randomisation and no bleeding requiring treatment at the TBS occurs any time prior to final fascial closure
- Proportion of subjects with no re-bleeding at the TBS

The following additional analysis will be performed for the FAS and Evaluable sets: Absolute time to haemostasis will also be analysed descriptively separately for subjects who achieved haemostasis with and without additional randomised treatments being required.

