| 1.3.6 | Operative data: Additional treatments – FAS | Reason for any additional treatment used at the TBS (d), time from randomization to re-bleed (c), and treatments applied (d); for patients re-treated with EVARREST, approximate length and width of EVARREST used (cm) (both c) | G2 |
| 1.3.7 | Operative data timings and other durations – FAS | Time in operating room (min), length of procedure (from first incision to last suture/staple) (min), length of procedure measured as time from first incision to initiation of fascial closure (when applicable) (min), time from screening visit to hospital admission (days), time from baseline visit to hospital admission (days), time from screening visit to surgery (days), time from baseline visit to surgery, and time from surgery to 30-day visit (days) (all c); For liver resections patients: time from start of liver resection to last suture/staple (min) and time from start of liver resection to initiation of final fascial closure (when applicable) (min) (both c) | G2 |
| 2 | Effectiveness data | | |
| 2.1 | Primary endpoint: Absolute time to hemostasis, elapsed from randomization | Includes analysis by treatment group and pediatric group, as well as by treatment group and age group; Includes analysis separately for subjects who achieved hemostasis with and without additional randomized treatments being required; Includes 95% CIs for median absolute time to hemostasis, reported separately for EVARREST and Control groups | |
| 2.1.1 | Primary effectiveness analysis: Absolute time to hemostasis, elapsed from randomization – FAS | Continuous data | G2 |
| 2.1.2 | Primary effectiveness analysis: Absolute time to hemostasis, elapsed from randomization – PP set (supportive analysis) | Continuous data | G2 |
| 2.2 | Secondary effectiveness endpoints | | |

| No | Title of table/figure | Notes | Shell ¹ |
|-------|---|---|--------------------|
| 2.2.1 | Hemostasis at 4 minutes following randomization and no bleeding requiring treatment at the TBS occurs any time prior to final fascial closure – FAS | Discrete data Includes 95% CI for proportion of subjects with hemostasis at 4 minutes separately for each group, as well as 95% CI for the ratio of proportions | G2 |

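### Does the split of time to haemostasis by additional randomised treatment leave subjects rescued by another method without a row?

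*SAP*

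**What the plan says.** The primary endpoint is the absolute time to haemostasis at the target bleeding site. The protocol synopsis says that all subjects will "have absolute time to haemostasis recorded regardless of any additional treatments", so a rescued subject still contributes a time.

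The split appears in three places with almost the same wording:

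- Protocol 8.3.1, for the FAS and Evaluable sets: "separately for subjects who achieved haemostasis with and without additional randomised treatments being required".
- SAP 8.2: "Absolute time to hemostasis will also be analyzed descriptively separately for subjects who achieved hemostasis with and without additional randomized treatments being required".
- The note to Table 14.2.1 in SAP 10.2.2: "Includes analysis separately for subjects who achieved hemostasis with and without additional randomized treatments being required".

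None of them defines the term. The table shells are in SAP Appendix 1, a separate attachment that was not available for this review.

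Other passages show that rescue need not be with the assigned product. The synopsis says that "if bleeding requiring treatment occurs after the 4 minute assessment the surgeon can revert to their standard of care for treatment". Protocol 7.1.3 lets the surgeon answer breakthrough bleeding in the EVARREST arm with more EVARREST or with standard of care. In the SURGICEL arm it mentions extra SURGICEL only before 4 minutes, for improper application, and standard of care after that. Protocol 6.4.1 adds: "The use of any other topical haemostats or fibrin sealant/fibrin sealant patch will be permitted".

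The 4-minute endpoint uses a broader term: "Any additional treatment at the TBS after the 4 minute endpoint will be considered a failure for the 4 minute secondary endpoint".

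**The concern.** Take a subject still bleeding at 4 minutes whose bleeding is then controlled only by a method other than the assigned product. A time to haemostasis is recorded, and three placements can be imagined:

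- **Literal:** no additional randomised treatment was given, so the subject joins the row without it, beside subjects who needed nothing more.
- **Loose:** the phrase is shorthand for any additional treatment, as in the 4-minute rule, so the subject joins the row with it.
- **Exclusive:** each row is taken to mean haemostasis achieved by the assigned product, so the subject appears in neither.

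Two programmers could therefore build different rows from the same data. The arms could also be affected unequally, because re-treatment with the assigned product after breakthrough bleeding is named only for EVARREST. A reader who takes the row without additional treatment as performance of the assigned product alone could be misled, more so for SURGICEL. This is also the only planned summary of time to haemostasis by additional treatment.

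**Working it through.** **Wording.** The sentence divides subjects who achieved haemostasis into those with and those without one thing. That division is exhaustive. A subject who received only another method had no additional randomised treatment and falls in the second row. The exclusive reading needs a third class that the sentence does not contain. The loose reading needs the word for randomised to be ignored, although protocol 7.1.3 gives it a natural meaning: re-application of EVARREST, or extra SURGICEL. The 4-minute rule does not settle the matter, because it defines failure of a different endpoint and applies only after 4 minutes.

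**Size, as an illustration only.** The plan has no figure to reproduce; SAP 8.2.1 states that no formal sample size calculation was made. Inputs:

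- n = 20 per arm (40 subjects, 1:1).
- Earlier-study haemostasis at 3 or 4 minutes (protocol section 1): 49.4% control, 89.9% EVARREST.
- f = share rescued, assumed equal to the share still bleeding then: 1 − 0.494 = 0.506 for SURGICEL; 1 − 0.899 = 0.101 for EVARREST.
- g = share of rescues made by another method only. The documents give no value, so 0, 0.5 and 1 are shown.

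Formulas for the size of the rows:

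- Literal: without = 20(1 − f) + 20fg; with = 20f(1 − g).
- Loose: without = 20(1 − f); with = 20f.
- Exclusive: without = 20(1 − f); with = 20f(1 − g); no row = 20fg.

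| Arm | g | Literal, without / with | Loose, without / with | Exclusive, without / with / no row |
|---|---|---|---|---|
| SURGICEL | 0 | 9.88 / 10.12 | 9.88 / 10.12 | 9.88 / 10.12 / 0 |
| SURGICEL | 0.5 | 14.94 / 5.06 | 9.88 / 10.12 | 9.88 / 5.06 / 5.06 |
| SURGICEL | 1 | 20.00 / 0 | 9.88 / 10.12 | 9.88 / 0 / 10.12 |
| EVARREST | 0 | 17.98 / 2.02 | 17.98 / 2.02 | 17.98 / 2.02 / 0 |
| EVARREST | 0.5 | 18.99 / 1.01 | 17.98 / 2.02 | 17.98 / 1.01 / 1.01 |
| EVARREST | 1 | 20.00 / 0 | 17.98 / 2.02 | 17.98 / 0 / 2.02 |

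Under the literal reading, the share of the without row rescued by another method is fg / (1 − f + fg): 0, 33.9% and 50.6% for SURGICEL; 0, 5.3% and 10.1% for EVARREST.

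These figures do not bound the effect. They omit subjects who are dry at 4 minutes and re-bleed later, and re-applications before 4 minutes. The rates pool adult, severe-bleeding and cardiovascular studies with other controls. Standard of care may itself be more of the control material, since the protocol introduction lists "topical absorbable haemostats such as oxidized regenerated cellulose, gelatin, or collagen" among the usual adjuncts, so g could be low in the SURGICEL arm.

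**What else is reported.** Table 14.1.3.6 gives the reason for additional treatment and the treatments applied. Listings 16.2.5.7 and 16.2.6.1 give additional treatments and time to haemostasis by subject. Re-treatment at the bleeding site is a safety endpoint.

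**The case for a change.** The best case for acting is that the whole primary analysis is descriptive, so calling this split descriptive does not make it unimportant. It sits in Tables 14.2.1.1 and 14.2.1.2, which feed the in-text table for the primary endpoint. Rescue by another method is foreseeable in both arms. Even the literal reading gives a row that mixes two kinds of subject, and the mix may differ by arm. The listings allow the groups to be separated only by hand and afterwards. A defining sentence would cost little.

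Much of this stands. The term is undefined in the visible text, and the literal row is mixed. What does not follow is that a subject lacks a row, or that a result depends on it. The rows are formed by an event after randomisation, so under any definition they are not a randomised comparison.

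Nor is a three-way split (none, assigned product only, any other method with or without assigned product) a clear gain. Its last category merges subjects with and without additional assigned product, so the split specified in protocol 8.3.1 could no longer be recovered. The cells would also be very small: with 20 EVARREST subjects and a rescue probability of 0.101, the chance of two or fewer rescued subjects is 0.671. One caveat remains: SAP section 7 lists the additional-treatment fields under bleeding after 4 minutes, so earlier re-applications may be less fully described.

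**Conclusion.** No change to the plan is needed. This is a missing definition in one supplementary descriptive breakdown, and the literal wording already gives analysts a workable rule. The unseen shells may also set the rows.

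The main summary of time to haemostasis, the confidence intervals for the medians and the 4- and 10-minute endpoints are the same under every reading. In the illustration the choice of reading moves 0 to 10.1 of 20 SURGICEL subjects and 0 to 2.0 of 20 EVARREST subjects between rows, or out of them. That range comes from an assumed rescue mix and includes no effect at all; the real extent is unknown.

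The point for the reader is one of interpretation: the row without additional randomised treatment is not necessarily time to haemostasis with the assigned product alone. The planned table of treatments applied and the by-subject listings show who received what.
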